Clinical Protocol BIOZEK

Title: **“Open label, Single-Center Study utilizing BIOZEK COVID-19 Antigen Rapid Test.”**

Comparison of Biozek COVID-19 Antigen Rapid test results performed on self-collected samples by the subjects, to results of COVID-19 RT-PCR as a standard of care.

Short title: Comparison of BIOZEK Antigen Rapid Test to COVID-19 RT-PCR.

Protocol Number: Biozek-ARTC-US/002/4-12-2021

Product: BIOZEK COVID-19 Antigen Rapid Test Cassette Nasopharyngeal Swab

BIOZEK COVID-19 Antigen Rapid Test Cassette Oral Fluid

Principal Investigator: [name]., PhD

Co-Principal Investigator: [name]

Study Coordinator: [name]

Version: Final 4.0

Date: June 1, 2021

CONFIDENTIALITY STATEMENT

The information contained in this document, particularly unpublished data, is the property or under control of Biozek medical and is provided to you in confidence as an investigator, potential investigator, or consultant, for review by you, your staff, and an applicable Institutional Review Board or Independent Ethics Committee. The information is only to be used by you in connection with authorized clinical studies of the investigational drug described in the protocol. You will not disclose any of the information to others without written authorization from Biozek Company, except to the extent necessary to obtain informed consent from those persons to whom the test may be performed.

1. Protocol Synopsis

Title:	
“Open label, Single-Center Study utilizing BIOZEK COVID-19 Antigen Rapid Test.”
 
Comparison of Biozek COVID-19 Antigen Rapid Test results performed on self-collected samples by the subjects, to results of COVID-19 RT-PCR as a standard of care.

Number of Subjects	
Planned:	Up to 250 Subjects, minimum of 30 positive and 30 negative tests.
Study Objectives:	
To assess sensitivity and specificity of BIOZEK COVID-19 Antigen Rapid Test on a self-collected sample and self-performed test by subject (nasopharyngeal swab and oral fluid).
 
To assess subject’s performance to collect samples and conduct BIOZEK COVID-19 Antigen Rapid Test.

Target Population:	Subjects, at least 18 years of age who desire a COVID-19 RT-PCR test. Subjects must meet inclusion and exclusion criteria.
Investigational Product:	
BIOZEK COVID-19 Antigen Rapid Test Cassette
 
Nasopharyngeal Swab
 
BIOZEK COVID-19 Antigen Rapid Test Cassette
 
Oral Fluid

Comparator:	
Type of test: RT-PCR
 
Name of test: Atila BioRad
 
BioFire
 
Luminex Aires

Study Design:	Up to 250 (30 positive and 30 negative) symptomatic subjects of age 18 or older that meet the inclusion and exclusion criteria and are willing to participate will be enrolled into the BIOZEK study. All subjects will be required to sign an informed consent form. A

study personnel will collect demographics information from the subjects.

A medical staff member will measure body surface temperature prior to performing any sample collection.

Subject will have 3 tests performed in a manner described below:

1. RT-PCR test (by medical staff prior to enrollment as a standard of care procedure). Additionally, Ct and/or FAM values will be requested. The Ct (cycle threshold) is defined as the number of cycles required for the fluorescent signal to cross the threshold (i.e., exceeds background level). The lower the Ct level the greater the amount of target nucleic acid in the sample. FAM (Fluorescein) is the most commonly used fluorescent dye attachment for oligonucleotides and is compatible with most fluorescent detection equipment.

2. BIOZEK COVID-19 Antigen Rapid Test Cassette- Nasopharyngeal Swab

(via self-collection - nasopharyngeal swab sample).

Nasopharyngeal samples will be collected via self-collection and the test will be performed by the subject. The participants will follow instructions for use provided by Biozek included with the test. The subject's performance during self-collection and test performance will be monitored and recorded in a performance form. Results in 15 minutes.

3. BIOZEK COVID-19 Antigen Rapid Test Cassette- Oral Fluid (via self-collection - oral fluid sample)

Oral fluid sample will be collected via self-collection and the test will be performed by the subject. The participants will follow instructions for use provided by Biozek included with the test. The subject's performance during self-collection and test performance will be monitored and recorded in a performance form. Results in 15 minutes.

Results will be retrieved from the RT-PCR test when available and all three samples will be analyzed and compared.

Criteria for Evaluation

Safety Criteria: During self-collection, the subject will be closely monitored according to standard of care and any adverse events will be captured.

Efficacy Criteria: Sensitivity and Specificity will be calculated separately for BIOZEK COVID-19 Antigen Rapid Test - on a self-collected, nasopharyngeal sample and for BIOZEK COVID-19 Antigen Rapid Test on the self-collected oral fluid sample.

Additionally, the result of each test performed by the subject will be compared to the RT-PCR test result.

End Points:

Sensitivity and Specificity of BIOZEK COVID-19 Antigen Rapid Test on self-collected nasopharyngeal sample.

Sensitivity and Specificity of BIOZEK COVID-19 Antigen Rapid Test on self-collected oral fluid sample.

Table of Contents

1. Protocol Synopsis	2
2. Introduction	6
3. Background	6
4. Study Objectives:	7
5. Investigational Product	7
6. Study Population	14
6.1 Inclusion Criteria	14
6.2 Exclusion Criteria	14
6.3 Sample Size	14
6.4 Confirmation of Patient Enrollment	14
6.5 Patient Identification	14
6.6 Removal, Replacement, or Early Withdrawals of Subjects	15
7. Overview of Investigational Plan and Study Administration	15
7.1 Enrollment	15
7.2 Material and Methods	15
7.3 Premature Discontinuation	16
7.4 Protocol Violations	16
7.5 Compliance	16
8. Data analysis.	17
9. Ethics	17
9.1 Hospital Ethics Committee/Institutional Review Board	17
9.2 Ethical Conduct of the Study	17
9.3 Subject Information and Consent	17
10. References	18

2. Introduction

Widespread testing is the cornerstone of COVID-19 control around the world. However, U.S. testing to identify people with infected SARS-CoV-2 has been slow to start and continues to lag. An important feature of SARS-CoV-2 is that it can be transmitted while a host is unaware of infection (asymptomatic). Epidemiologic evidence has demonstrated that pre-symptomatic and asymptomatic transmission of virus has driven the current epidemic¹. Antigen tests have a great potential for screening asymptomatic people². To limit outbreaks, testing is needed to identify as many individuals who are transmitting infection as quickly as possible. Antigen Tests have the potential to readily identify an individual who is at or near peak infection. Rapid Tests, while less sensitive, perform best during the early stages of COVID-19 infection; when viral load and potential for spread is high.

There is an unmet need to provide broad testing that can serve high risk and low resource communities. The FDA's authorization for antigen tests for home use is helping to expand Americans' access to testing, reducing the burden on laboratories and test supplies³. The Biozek Antigen Rapid Test can be easily performed by untrained personnel with results in less than 15 minutes. The increased potential for repeated testing, remote or at home testing, could help contain the COVID-19 pandemic.

3. Background

In December 2019, an outbreak emerged identifying a novel coronavirus, severe acute respiratory syndrome coronavirus 2 (SARS-CoV-2). The World Health Organization (WHO) declared it a global pandemic in March 2020. Testing in the U.S. appeared to be insufficient for optimal early containment of the virus. With the resurgence of the disease (COVID-19), the U.S. has recently seen the highest number of hospitalizations since the beginning of the pandemic and rates are expected to increase in future weeks⁴. Given the continued community transmission of SARS-CoV-2 in the US, there has been sustained focus on the role of testing to reduce the spread. Presently, the gold standard polymerase chain reaction (PCR) test is used to diagnose COVID-19 by detecting the presence of specific genetic material of the virus. PCR test requires laboratory processing and it may take days to obtain results. In turn, an individual could be negative at time of testing but positive by the time the result is returned⁵. PCR testing is performed by a trained healthcare professional at an approved testing facility. In contrast, The BIOZEK Rapid Antigen Test detects specific proteins on the surface of the virus and it can be self-administered. Results are generated in 15 minutes and can be performed at home or any remote location. In efforts to meet the exponential demand in testing, the introduction of a new and effective Rapid Test could potentially end the spread of COVID-19.

4. Study Objectives:

To assess sensitivity and specificity of BIOZEK COVID-19 Antigen Rapid Test on a self-collected sample and self-performed test by subject (nasopharyngeal swab and oral fluid).

To assess subject's performance to collect samples and conduct BIOZEK COVID-19 Antigen Rapid Test.

5. Investigational Product

[figure not shown]
The BIOZEK COVID-19 Antigen Rapid Test Cassette is a qualitative membrane-based immunoassay for the detection of SARS-CoV-2 nucleocapsid protein antigens in human nasopharyngeal swab specimens and in oral fluid specimens. SARS-CoV-2 antibody is coated in the test line region. During testing, the specimen reacts with SARS-CoV-2 antibody-coated particles in the test. The mixture then migrates upward on the membrane by capillary action and reacts with the SARS-CoV-2 antibody in the test line region.

If the specimen contains SARS-CoV-2 Antigens, a colored line will appear in the test line region as a result of this. If the specimen does not contain antigens to SARS-CoV-2, no colored line will appear in the test line region, indicating a negative result. To serve as a procedural control, a colored line will always appear in the control line region, indicating that the proper volume of specimen has been added and membrane wicking has occurred.

If the specimen contains SARS-CoV-2 Antigens, a colored line will appear in the test line region as a result of this. If the specimen does not contain antigens to SARS-CoV-2, no colored line will appear in the test line region, indicating a negative result. To serve as a procedural control, a colored line will always appear in the control line region, indicating that the proper volume of specimen has been added and membrane wicking has occurred.

Name	Description	Dosage (Swab)	Dosage (Oral Fluid)
Goat anti-mouse IgG	Liquid, capture in the NC membrane	0.150-0.300 μ g/test	0.150-0.300 μ g/test
Mouse IgG	Liquid, detection in the label pad	0.050-0.200 μ g/test	0.050-0.200 μ g/test
Mouse anti-Nucleocapsid protein	Liquid, capture in the NC membrane	0.0100-0.400 μ g/test	0.080-0.800 μ g/test
Mouse anti-Nucleocapsid protein	Liquid, detection in the NC membrane	0.080-0.350 μ g/test	0.100-0.400 μ g/test

Table.1 Amounts, concentrations, or quantities of antibodies in each test.

As shown in illustration above, the specimen (A) migrates via capillary action along the membrane to react with the colored conjugate (B). COVID-19 antigen present in the specimen binds to the conjugate, forming a colored antibody-antigen complex. The Anti-SARS-CoV2 immobilized in the test zone of the membrane captures the test region (C). The formation of a

visible colored line in the test region indicates a positive result (C). The absence of a colored line in the test zones suggests a negative result. In the control zone of the membrane, immobilized reagents capture colored conjugate regardless of test specimen composition. The resulting visible colored band (D) confirms the control line.

Materials provided in the BIOZEK-COVID-19 Antigen Rapid Test kit includes:

Nasopharyngeal Swab: Test cassettes, Sterile Swabs, Extraction tubes and tips, Extraction Buffer, Workstation, Package Insert.

Materials Provided

Description	Option 1	Option 2	Option 3
Test Cassettes	30	30	30
Sterile Swabs	30	30	30
Work Station	1	1	1
Package Insert	1	1	1
Extraction Buffer (NaCl 5g/L, Tris 3g/L, Proclin300, 0.02%, BSA 5g/L, TritonX-100 2g/L, pH 8.5)	in pre-filled integrated buffer tube	30	/
	in disposable buffer vial	/	30
	in 10mL buffer bottle	/	2
Extraction Tubes and Tips	/	30	30

Materials Required But Not Provided

- Timer
- Specimen Transport Tubes

Disposable sampling Swab:

Production: Jiangsu Hanheng Medical Technology Co

Place of Origin: Jiangsu, China

Brand Name: HanHeng

Disinfecting Type: EO sterilization

Size: 15.2cm with 8.5cm breakpoint

Shelf Life: 5 years

Material: 100% Nylon, Nylon floss tip +PP rod

Quality Certification: ce

Safety standard: EN 149 -2001+A1-2009

Product name: nasal swab

Property: sample collection

Certificate: CE/ISO13485

[figure not shown]
Product Certification

CE Certified. Valid from 2019-11-25 until 2024-05-27

Oral Fluid: Test cassette, Collection Device (Funnel, Extraction Tube and Tip, Dropper), Extraction Buffer, Biosafety Bag, Workstation, Package Insert, Instruction for Use.

Content

Materials Provided

Description		Quantity
Test Device		20
Collection Device	Funnel	20
	Extraction Tube & Tip	20
	Dropper	20
Extraction Buffer (NaCl 5g/L, Tris 3g/L, TritonX-100 5g/L, BSA 5g/L, Proclin300 0.02%, pH 8.5)		20
Biosafety Bag		20
Work Station		1
Package Insert		1
Instruction Guide		1

[figure not shown]
Materials Required But Not Provided

Description of Test Steps:

Biozek Covid-19 Antigen Rapid Test

[figure not shown]
Specimen Collection - Nasopharyngeal Swab

1. Insert a provided sterile swab into the nostril of the patient carefully, reaching the surface of the posterior nasopharynx.
2. Swab over the surface of the posterior nasopharynx gently.
3. Withdraw the sterile swab from the nasal cavity.

Nasal Swab Specimen Collection

1. Insert a sterile swab less than one inch (about 2 cm) into a nostril (until resistance is met at the turbinate).
2. Rotate the swab 5-10 times against the nasal wall. Using the same swab repeat the collection procedure with the second nostril.
3. Withdraw the sterile swab, avoid excess volume and high-viscous nasal discharge.

[figure not shown]

Caution: If the swab stick breaks during specimen collection, repeat specimen collection with a new swab.

Specimen Extraction –Nasopharyngeal Swab

Only the extraction buffer provided in this kit is to be used for specimen extraction.

1. Peel off the sealing on the extraction tube with extraction buffer inside.
2. Place the swab specimen into the extraction buffer, for better mixture and extraction to release the antigen, rotate the swab for approximately 10 seconds while pressing the swab head against the inner wall of the tube at least 5 times to release the antigen.
3. Remove the swab while squeezing the swab head against the inner wall of the tube to get maximum solution left inside the extraction tube. Dispose of the used swab in your biohazard waste.
4. Fit the tip onto the top of the extraction tube. Use extracted sample solution as final sample for testing as soon as possible.

NOTE: The storage of the extracted specimen is stable for 2 hours at room temperature or 24 hours at 2-8°C.

[figure not shown]
Testing Procedure – Nasopharyngeal Swab

Allow the test cassette, extracted sample solution and/or controls to equilibrate to room temperature (15-30°C) prior to testing.

1. Remove the test cassette from the sealed foil pouch and use it within one hour. Best results will be obtained if the test is performed immediately after opening the foil pouch.
2. Shake the extracted sample solution to mix it well. Invert the sample extraction tube and add 3 drops of the Extracted Sample Solution (approx.75-100µL) to the specimen well(S) of the

cassette. Start the timer.

3. Wait for the red line(s) to appear and read the result at 15 minutes. Do not interpret the result after 20 minutes.

[figure not shown]

Interpretation of results - Nasopharyngeal Swab

POSITIVE: * Two red lines appear. One red line should be in the control region (C) and another red line should be in the test region (T). Positive result in the test region indicates detection of COVID-19 antigens in the sample. *NOTE: Red color line intensity in the test region (T) will vary based on the amount of COVID-19 antigen present in the sample. Any shade of red color in the test region (T) should be considered positive.

[figure not shown]
NEGATIVE: One red line appears in the control region (C). No apparent red line appears in the test region (T) indicates a negative COVID-19 antigen test result.

INVALID: No red line appears in the control region (C). Insufficient specimen volume or incorrect procedural techniques are the most likely reasons for control line failure. Review the procedures and repeat the test with a new cassette. If the problem persists, discontinue using the test kit immediately and contact your local BIOZEK products distributor.

Specimen Collection - Oral Fluid

[figure not shown]
Content

Advise the patient not to consume food, beverages, chewing gum, tobacco, and other substances at least 10 minutes prior to specimen collection.

Step 1

Connect the plastic tube (number 2) to the mouthpiece (number 1). Press the plastic tube as far as possible into the mouthpiece.

Step 2

If you are having trouble collecting saliva in your mouth, try closing your mouth and wiggling your tongue. Gently rubbing the outside of your cheeks, just behind your back teeth. Making chewing motions with your mouth.

NOTE: We recommend carrying out this step in the morning.

Step 3

Spit the oral fluid into the mouthpiece. There should be about 0.5 ml of liquid in the plastic tube. This corresponds to the bottom line on the plastic tube.

[figure not shown]

Step 4a

Remove the mouthpiece (number 1) and dispose of it in the specimen bag (number 8). Place the plastic tube in the holder (number 6).

Step 4b (only follow this step if there is too much saliva)

[figure not shown]
More than 0.5 ml of liquid? Take the pipette (number 3). Press and hold the bulb until the pipette protrudes into the solution of the plastic tube (1). Release the balloon slowly, so that the pipette sucks up the solution (2). Bring the liquid level to the bottom line (0.5 ml).

Specimen Extraction – Oral Fluid

Step 5

Take the buffer (number 4) and remove the seal at the top (by cutting/breaking it). Squeeze the contents of the buffer into the plastic tube (number 2) containing the mucus/spittle.

[figure not shown]

Step 6

Put the cap (number 5) on the plastic tube (number 2).

Step 7

[figure not shown]
Knead the bottom of the plastic tube firmly (number 2) for 10 seconds to mix the buffer well with the mucus/spit.

Testing Procedure – Oral Fluid

Step 8

Tear open the test package and remove the test cassette. Turn the plastic tube (number 2) upside down and let 2 drops of liquid fall into the opening next to the letter S on the cassette (number 7).

[figure not shown]

Step 9

Wait 15 minutes.

Step 10

Read the result Positive: You have tested positive for COVID-19 antigens, so please contact your doctor. Negative: You have tested negative, so the test did not detect any antigens in your sample. However, if you have COVID-19 related complaints, please contact your doctor. Invalid: The test cannot be displayed, so contact your supplier for further instruction. Do not throw the test away. If necessary, take a Positive Negative Invalid photo of the contents and packaging.

How to Store Biozek COVID-19 Antigen rapid test.

Store the BIOZEK COVID-19 Antigen Rapid Test Cassette packaged in the sealed pouch and extraction buffer at room temperature or refrigerated (2-30°C). The test and extraction buffer are stable through the expiration date printed on the sealed pouch and buffer label. The test must remain in the sealed pouch until use. DO NOT FREEZE. Do not use the kit beyond the expiration date. Do not use the kit if the package of the test cassette or buffer is damaged.

6. Study Population

6.1 Inclusion Criteria

Subjects must be ≥ 18 years of age and have had an RT-PCR test performed prior to enrollment. Subjects must be able to understand and willingly sign a written informed consent. Additionally, participants need to meet at least 1 of the criteria listed below:

- Currently experiencing symptoms of COVID-19.
- Be clinically diagnosed or suspected to have COVID-19.
- Recent past (3 weeks) exhibited symptoms of COVID-19.
- Be capable of performing a self-collection of a nasopharyngeal sample with use of nasal swab kit.
- Be capable of performing a self-collection of an oral fluid sample with use of oral fluid collection kit.
- Interacted with a COVID-19 positive individual.

6.2 Exclusion Criteria

Subjects who meet any of the following exclusion criteria may not be enrolled in this study:

- Cannot perform self-collection of a nasopharyngeal sample with use of nasal swab kit.
- Cannot perform self-collection of an oral fluid sample with use of oral fluid collection kit.
- Have a deviated nasal septum.
- Cognitively impaired individuals resulting in the inability to provide informed consent

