6.3 Sample Size

Up to 250 subjects will be enrolled in the study. The study shall be continued until at least 30 positive and 30 negative tests results are obtained.

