7.2 Material and Methods

The Enrollment population consists of up to 250 (minimum of 30 positive and 30 negative samples) symptomatic patients. Enrollment will take place at the subject's home during scheduled visits to patients appointed for an RT-PCR test, as the standard of care procedure, performed by a medical staff member. Medical staff members will perform the RT-PCR test and the samples will be sent to A2Z Diagnostics Laboratory. The results will be available in 1-3 days. Results including Ct and/or FAM values of the RT-PCR test from subjects enrolled to the study will be collected by study personnel.

After completion of the RT-PCR Test, the patients will be asked if they are willing to participate in the BIOZEK Study. If the subject is age 18 or older and meets the inclusion and exclusion criteria, they will sign an Informed Consent Form and will be enrolled into the BIOZEK study. A study personnel will collect demographics information from the subjects; in addition, they will take the subject's body's surface temperature and capture it in the CRF.

Subject will perform 2 additional tests performed in a manner described below:

1. BIOZEK COVID-19 Antigen Rapid Test Cassette-Nasopharyngeal Swab (via self-collection - nasopharyngeal swab sample),

Nasopharyngeal samples will be collected via self-collection and the test will be performed by the subject. The participants will follow instructions for use provided by Biozek included with the test. The subject's performance during self-collection and test performance will be monitored and recorded in a performance form. Results in 15 minutes.

2. BIOZEK COVID-19 Antigen Rapid Test Cassette-Oral Fluid (via self-collection - oral fluid sample)

Oral fluid sample will be collected via self-collection and the test will be performed by the subject. The participants will follow instructions for use provided by Biozek included with the

test. The subject's performance during self-collection and test performance will be monitored and recorded in a performance form. Results in 15 minutes

Test Results

After interpreting the results, the coordinator will take an image of the cassette to be recorded and captured in the CRF. Compliant to all procedures required for disposal of biohazardous waste.

Results will be retrieved from the PCR test when available and all three samples will be analyzed and compared.

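### The test is presented as usable by untrained people, but trained subjects are eligible and the protocol does not require training status to be recorded or used in the analysis

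*Combined protocol and SAP*

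**What the plan says.** The Introduction (section 2) describes the intended user: "The Biozek Antigen Rapid Test can be easily performed by untrained personnel with results in less than 15 minutes". The Background (section 3) contrasts this with PCR, which needs a trained professional.

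Section 4 has two objectives. The first is sensitivity and specificity when the subject both collects the sample and runs the test. The second reads "To assess subject's performance to collect samples and conduct BIOZEK COVID-19 Antigen Rapid Test".

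On eligibility, section 6.1 requires adult age, a prior RT-PCR test and consent, and continues "Additionally, participants need to meet at least 1 of the criteria listed below". The six listed items concern symptoms, diagnosis, exposure and ability to self-collect. Section 6.2 opens with "Subjects who meet any of the following exclusion criteria may not be enrolled in this study" and lists inability to collect either sample (two items), a deviated nasal septum, and cognitive impairment that prevents consent.

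On data, section 7.1 mentions an information form for patient details. Section 7.2 says "A study personnel will collect demographics information from the subjects" and adds body surface temperature. For each Biozek test it says "The subject's performance during self-collection and test performance will be monitored and recorded in a performance form". The contents of these forms are not given.

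Section 8 plans a comparison with RT-PCR and the calculation of sensitivity and specificity. It plans nothing by type of user.

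**The concern.** The steps in section 5 depend on technique. The swab has to reach the back of the nasopharynx, the extract has to be mixed and a set number of drops applied, and a faint test line has to be read as positive. For the swab test, section 5 itself names handling errors among the most likely causes of an invalid result. Someone who takes swabs or runs assays at work can plausibly do these things better than someone following the leaflet for the first time.

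A nurse or laboratory technician booked for an RT-PCR test is eligible as the criteria stand. If such subjects are pooled with everyone else, the objective 2 results and the self-performed accuracy in objective 1 describe a mixture, and the plan has no step that reports the lay part of it. The expected direction favours the product, most clearly for performance and sensitivity; for specificity the direction is less obvious. What is at stake is whether the results support the use by untrained people on which the rationale rests.

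**Working it through.** **Check of the text.** The protocol's provisions were set against what would be needed to describe lay users.

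| Needed | Where it would appear | Found |
|---|---|---|
| Criterion on training | 6.1, 6.2 | None |
| Required data item on training | 7.1, 7.2 | None named; form contents not given |
| Analysis by type of user | Efficacy criteria in the synopsis; section 8 | None |

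**Size of the possible overstatement.** The protocol has no figure to reproduce: it gives no share of trained subjects, no expected sensitivity or specificity, and no precision target. All rates and shares below are assumptions.

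Let f be the share of trained subjects.

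- Pooled rate = (1 - f) x lay rate + f x trained rate.
- Overstatement = f x (trained rate - lay rate).

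With f from 10% to 30% and a gap of 10 to 20 points:

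- Lowest: 0.10 x 10 = 1 point.
- Highest: 0.30 x 20 = 6 points.
- Example: lay 75%, trained 90%, f = 20% gives 0.8 x 75% + 0.2 x 90% = 78%, which is 3 points above the lay rate.

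Wider assumptions show how far the answer depends on them, with trained users at 95%:

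- Lay 90%, f = 10%: 0.10 x 5 = 0.5 points.
- Lay 70%, f = 50%: 0.50 x 25 = 12.5 points.
- f near zero, or no gap: no overstatement.

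**What a lay-user analysis could show at the minimum.** Section 6.3 says "The study shall be continued until at least 30 positive and 30 negative tests results are obtained". Taking this as 30 RT-PCR positives, with exact (Clopper-Pearson) 95% intervals:

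- All subjects, 24/30 = 80%: 61% to 92%.
- f = 20% leaves 0.8 x 30 = 24 lay positives; 19/24 = 79%: 58% to 93%.
- The other 6 positives would be trained. Even at 6/6 the lower limit is 0.025^(1/6) = 54%.

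Losing six positives widens the lay interval only a little, from about 31 to 35 points. The trained and lay intervals overlap heavily, so a comparison between the groups would not be interpretable.

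If 30 positives were wanted among lay users alone, the total would be 30/(1 - f), rounded up: 34, 38 or 43 positives for f = 10%, 20% or 30%.

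**The case against.** The best case for leaving the plan alone is that lay use is background, not the estimand. The statement about untrained users stands in the Introduction. The objectives speak of the subject, the endpoints are sensitivity and specificity on self-collected samples, and the target population is adults who want an RT-PCR test. A health worker who wants a test belongs to that population, so a pooled estimate is biased only against a lay-only target that the protocol never sets. This stands in part: there is no internal contradiction. It does not remove the gap between the use that motivates the study and the people whose results it will report.

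Four stronger readings are tempting, and the documents do not support them.

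- A reader might infer that training status will not be recorded at all. The information form, the CRF and the performance form are not in the documents and the demographic items are not listed, so occupation may be captured. What can be said is that the protocol does not require it and plans no use of it.
- A reader might infer that lay results can never be separated or the omission repaired. Training before the visit is a historical fact and subjects are numbered, so a later query is conceivable. It would be inferior to asking at enrolment, but it is not shown to be impossible.
- A reader might class experienced self-testers with trained workers. The Introduction counts repeated and home testing among the product's benefits, so people who have used a rapid test before fall within the intended use.
- A reader might take 1 to 6 points as an estimate. Nothing in the protocol anchors the share or the gap. Recruitment at home visits for RT-PCR may bring in few trained people.

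It is also fair to say that sampling error at 30 positives far exceeds 1 to 6 points. That limits how visible the effect would be. It does not make the effect average out, because an overstatement of this kind does not shrink as the sample grows.

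**Conclusion.** The point holds as a modest, inexpensive improvement. The protocol promotes use by untrained people, admits people with health-care or laboratory training, and neither requires that status to be recorded nor uses it in the analysis. As written, it has no planned way to show what lay users achieve, and pooled results could overstate it.

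The size is unknown and may be negligible. The figure of 1 to 6 points rests wholly on an assumed trained share of 10-30% and an assumed advantage of 10-20 points. The upward direction is plausible because the procedure depends on technique, but the documents do not demonstrate it, and for specificity it is uncertain. The conclusion rests on the protocol text and would weaken if the unseen forms already ask about occupation or training, although the planned analysis would still make no use of the answer.

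**What to change.** Add one required CRF item: current or former health-care or laboratory training that includes specimen collection or diagnostic testing (yes/no). In section 8, name subjects who answer no as the primary population for objective 2. Report sensitivity and specificity for them as well as for all subjects, each with exact 95% confidence intervals.

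Alternatively, add one line to section 6.2 that excludes such trained subjects. The minimum of 30 positives and 30 negatives then applies to lay users without any change.

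Prior rapid-test use may be recorded and described, but it should not place a subject outside the intended population.

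The cost is one form item and a sentence in section 8, or one eligibility line. A few subjects leave the lay-user analysis or the study, and the reported figures may be slightly less favourable. The plan should say that no trained-versus-lay comparison is intended, because at 30 positives it would be too imprecise to interpret. If training is recorded rather than excluded, the sponsor should also state whether the minimum counts apply to all subjects or to lay users. The second choice needs the additional positives shown above, and additional negatives by the same formula.
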